
a. Pre-screening and screening visits may be completed on the same day.
 
b. Agreeing to the genetic sample consent is not required for study participation.
 
c. A pre-screening plasma fibrinogen measurement is only required for participants with 1 COPD exacerbation in the prior year.
 
d. Smoking status /history assessed at screening; smoking status rechecked at Visit 2
 
e. Includes substance usage, past and present medical conditions and family history of premature CV disease.
 
f. See inclusion/exclusion criteria for CXR screening requirement
 
g. Hepatitis B (HBsAg) and Hepatitis C (HepC antibody) testing is required. If testing otherwise performed within 3 months prior to the first dose of study treatment, testing at screening is not required. Hepatitis C RNA testing is optional; however a confirmatory negative Hepatitis C RNA test must be obtained, to be able to enrol participants with positive Hepatitis C antibody due to prior resolved disease.
 
h. Participant's clinical status should be reviewed.
 
i. Pregnancy testing only required for women of child bearing potential (WOCBP). A positive urine pregnancy test requires confirmation with a serum pregnancy test.
 
j. E-RS:COPD is a subset of EXACT-PRO and is not a separate assessment.
 
k. Rescue medication use will be assessed via e-diary and MDI sensor.
 
l. The Clinic Visit PROactive Physical Activity in COPD tool will be assessed in a subset of approximately 50% of study participants
 
m. Pre-dose PK samples will be collected in all participants at Visits 3, 6, 7, and 10. In a subset of participants (approx. 50 participants at each dose level) at Visit 3, PK samples will be collected at pre-dose, 0.5, 1, 2, 4, 6, 8, 10, 12 hours post-dose. In a subset of participants (approx.. 50 participants at each dose level) at Visit 10, PK samples will be collected at pre-dose, 0.5. 1. 2. 4. 6, 8, 10, 12 hours post-dose.
													

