6.1. Inclusion Criteria

Participants are eligible to be included in the study only if all of the following criteria apply:

Age

1. Participant must be 40 to 80 years of age inclusive, at the time of signing the informed consent.

Type of Participant and Disease Characteristics

2. Participants who have COPD (postbronchodilator FEV1/FVC ratio < 0.7 and FEV1 % predicted $\geq 40\%$) based on American Thoracic Society (ATS)/European Respiratory Society (ERS) current guidelines [Celli, 2004]. Participants with a historical diagnosis of asthma may be included so long as they have a current diagnosis of COPD.
3. History of respiratory symptoms including chronic cough, mucus hypersecretion, and dyspnea on most days for at least the previous 3 months prior to screening.
4. Participants with a documented history of COPD exacerbation(s) in the 12 months prior to study participation (screening) meeting at least one of the following criteria:
 - ≥ 2 COPD exacerbations resulting in prescription for antibiotics and/or oral corticosteroids or hospitalization or extended observation in a hospital emergency room or outpatient center
 - 1 COPD exacerbation resulting in prescription for antibiotics and/or oral corticosteroids or hospitalization or extended observation in a hospital emergency room or outpatient center and a plasma fibrinogen concentration at screening ≥ 3 g/L (300 mg/dL)
5. Smoking history: current and former smokers with a cigarette smoking history of ≥ 10 pack years (1 pack year = 20 cigarettes smoked per day for 1 year or equivalent). Current smokers are defined as those who are currently smoking cigarettes (i.e. have smoked at least one cigarette daily or most days for the month prior to Visit 1). Former smokers are defined as those who have stopped smoking for at least 6 months prior to Visit 1. Note: pipe and/or cigar use cannot be used to calculate smoking pack-year history.
6. Participants must have the ability and willingness to use an electronic diary (log pad) on a daily basis.

Weight

7. Body weight ≥ 45 kg

Sex

8. Male or female.

a. Male participants:

A male participant must agree to use contraception as detailed in [Appendix 5](#) of this protocol during the treatment period and for at least 60 hours after the last dose of study treatment, corresponding to approximately 6 half-lives (which is the time needed to eliminate any teratogenic study treatment) and to refrain from donating sperm during this period.

b. Female participants:

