## 4. ANALYSIS POPULATIONS

### 4.1. Strategic Interim Analysis

Population	Definition / Criteria	Analyses Evaluated
All Subjects (ALLSUB)	
 
All participants screened and for whom a record exists on the study database.
 
	
 
Participant disposition
 
Reasons for withdrawal prior to randomization
 
Inclusion/exclusion/randomization criteria deviations for non-randomized participants
 
AEs and SAEs for non-randomized participants
 

Intent-to-treat (ITT)	
 
All randomized participants apart from those who were randomized in error (i.e. were also recorded as screen or run-in failures and did not receive a dose of study treatment).
 
Any participant who receives a treatment randomization number will be considered to have been randomized.
 
Randomized participants will be assumed to have received study medication unless definitive evidence to the contrary exists.
 
Data will be reported according to the randomized treatment.
 
	
 
Selected efficacy displays as described in Section 7
 
Strategic Interim only
 

Modified Intent-To-Treat (mITT)	
 
Same as the Intent-to-treat population, but this population will be 'modified' in that all data summaries and analyses for this population will be based on the actual treatment received, if it is different to the randomized treatment.
 
If any participant received more than one treatment during a treatment period, their data will be reported according to the treatment they received for the longest period of time.
 
	
 
Study Population
 
Safety
 

Per Protocol (PP)	
 
All participants from the mITT population who did not have a protocol deviation considered to impact efficacy
 
	
 
Efficacy
 

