## 5.4.2. Examination of Subgroups

The subgroups listed below will be used in statistical analyses as described in Section 7.

Subgroup	Categories
Season	Spring, Summer, Fall, Winter (see Section 14.6.3)
Country	Australia, Canada, Germany, Korea, Netherlands, Poland, Romania, Spain, US
Exacerbation history	History of $\geq 2$ moderate/severe exacerbations vs $< 2$ moderate/severe exacerbation
COPD medication at Baseline	ICS+LABA+LAMA vs. ICS+LABA vs. LABA+LAMA vs. Other COPD medication
ERS10	Baseline E-RS: COPD Total Score $< 10$ , $\geq 10$
CAT10	Baseline CAT Score $< 10$ , $\geq 10$
Smoking status at Screening	Current, Former
% predicted FEV1 at Screening	$< 50\%$ , $\geq 50\%$
CMH status at baseline	CMH+, CMH- (see Section 14.6.2)

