### 7.1. Primary Efficacy Analyses

#### 7.1.1. Month 6 E-RS: COPD Total Score Dose-Response Analysis

The estimand is the effect of actual treatment in the population of participants who did not experience a protocol deviation considered to impact efficacy and completed six months of treatment.

A Bayesian dose response model will be applied to the change from baseline to Month 6 and used to estimate the treatment difference between placebo and each dose.

The dose-response model will be fitted using Bayesian techniques with non-informative priors for E0 and Emax and a functional uniform prior (FUP) for ED50 and the slope parameter, m ([Bornkamp, 2014](#)). The rationale for this choice of inference is that the FUP shrinks the dose-response towards a flat line throughout the dose range, therefore providing more conservative estimates of the dose-response relationship compared to maximum likelihood.

For the strategic interim, the posterior predictive probability of success (PPS) at the end of the study will be calculated for each dose using the formula suggested by Spiegelhalter et al. ([Spiegelhalter, 2004](#)) as follows:

$$PPS = \Phi \left[ \frac{\sqrt{(m+n)} \frac{(-my_m)}{\sigma_{trt\ diff}} + \sqrt{\frac{m}{n}} z_{0.9}}{\sqrt{mn}} \right]$$

Where m is the average number of participants with Month 6 data in the placebo and comparative dose arm, n is the average number of participants yet to be observed (assuming 90% of participants, rounded to the nearest integer, in each treatment group will provide month 6 data at end of study. If the actual number of participants at month 6 exceeds this, the actual number will be used),  $y_m$  is the posterior mean difference from the fitted model, and  $\sigma_{trt\ diff}$  is the standard deviation (SD) of the posterior mean difference.

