**7.2.1.5. Statistical Analyses / Methods**

**7.2.1.5.1. Statistical Methodology Specification**

Endpoint / Variables

 
• Annual rate of On-treatment moderate/severe HCRU exacerbations
 
• Annual rate of On-treatment EXACT events
 

Model Specification

 
• Bayesian generalized linear model assuming a negative binomial distribution for the underlying exacerbation rate with a log link function
 
• Terms in the model:             
 
○ Response: number of on-treatment, moderate/severe HCRU exacerbations or EXACT events per participant.
 
○ Categorical: treatment group, gender, exacerbation history (<math>\leq 1</math>, <math>\geq 2</math> moderate/severe), smoking status (screening), country
 
○ Continuous: post-bronchodilator % predicted FEV1 (Screening)
 
○ An offset to account for the length of time on treatment for each participant will be
 
 
 

- included in the model as  $\log_e$  (length of time) as defined in Section 14.6.3.
- Non-informative priors will be used for all modelling parameters. Wherever possible conjugate priors will be utilised.
- All the terms in the model will follow a normal distribution with a mean of 0 and a SD of 100, except for dispersion which follows a gamma distribution with shape and inverse scale of 0.001.
- Three chains will be used to calculate the gelman-rubin R statistic:
  - Chain 1: The starting value for all covariates in the model will be the maximum likelihood estimation (MLE), except dispersion which will be 0.1.
  - Chain 2: The starting value for all covariates in the model will be 130% of the MLE, except for dispersion which will be 0.2.
  - Chain 3: The starting value for all covariates in the model will be 70% of the MLE, except for dispersion which will be 0.4.
- The seeds used to for the three chains were generated using the ranuni function in SAS and are listed in Section 14.5.2.
- Burn-in 2000, thin 5, and 10,000 MCMC samples will be generated for 2000 retained samples

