## 14. APPENDICES

### 14.1. Appendix 1: Protocol Deviation Management and Definitions for Per Protocol Population

#### 14.1.1. Exclusions from Per Protocol Population

A participant meeting any of the following criteria will be excluded from the Per Protocol population:

Number	Exclusion Description
01	Inclusion #2 – FEV1/FVC ratio $\geq 0.70$ or % predicted FEV1 $< 40\%$ at Screening
02	Inclusion #4 – $< 2$ historical exacerbations or one historical exacerbation with screening fibrinogen $< 3$ g/L
03	Inclusion #5 - Smoking history of $< 10$ pack years at Screening
04	Exclusion #4 - Screening visit is less than 14 days since the completion of a course of antibiotics or oral steroids for a COPD exacerbation
05	Exclusion #14 - Use of PDE4 inhibitors within 30 days of Screening
06	Exclusion #26 - Oxygen use that is not PRN at Screening

At the strategic interim a participant meeting any of the following criteria will be excluded from the Per Protocol population:

Number	Exclusion Description
07	Xanthines at any time between the day after screening and end of treatment
08	PDE4 inhibitors at any time between screening and end of treatment
09	Chronic use (more than 3 months) of erythromycin or azithromycin for between screening and end of treatment
10	Participants who stopped study medication for more than 14 days
11	Blind broken

For the final analysis a participant meeting any of the following criteria will have data excluded from the time of the deviation. If a prohibited medication is taken prior to randomisation the participant will be excluded from the Per Protocol population.

Number	Exclusion Description
07	Xanthines at any time between the day after screening and end of treatment
08	PDE4 inhibitors at any time between screening and end of treatment
09	Chronic use (more than 3 months) of erythromycin or azithromycin between screening and end of treatment
10	Participants who stopped study medication for more than 14 days will be excluded from the PP analyses from the time they stopped taking study medication.
11	Data excluded from date of breaking of blind.

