
 
Exacerbations (historical) will be classified as follows: 
 
Mild: Managed without oral/systemic corticosteroids and/or antibiotics (not involving hospitalisation)
 
Moderate: Requiring oral/systemic corticosteroids and/or antibiotics (not involving hospitalisation)
 
Severe: Requiring hospitalisation
 
Moderate/severe: Requiring oral/systemic corticosteroids and/or antibiotics or hospitalisation.
 
 
 
The total number of moderate/severe exacerbations will be categorized as ≤1, ≥2 for inclusion as a covariate in statistical models.
 

GOLD Grade 1-4 at Screening

 
Participants will be classified into Global Initiative on Obstructive Lung Disease (GOLD) Grades 1-4 using the post-bronchodilator percent predicted FEV1 assessment at Screening: 
 
GOLD Grade 1 (Mild): percent predicted FEV1 ≥80%
 
GOLD Grade 2 (Moderate): 50%≤ percent predicted FEV1 <80%
 
GOLD Grade 3 (Severe): 30%≤ percent predicted FEV1 <50%
 
GOLD Grade 4 (Very Severe): percent predicted FEV1 <30%
 
 
 

GOLD Grade A-D at Screening

 
Participants will be classified into GOLD Grades A-D definitions as follows: 
 
A. Low risk, less symptoms: baseline CAT < 10 AND GOLD Grade 1-2 AND ≤1 exacerbation; (no hospitalizations for exacerbations), prior year.
 
B. Low risk, more symptoms: baseline CAT >= 10 AND GOLD Grade 1-2 AND ≤1 exacerbation (no hospitalizations for exacerbations), prior year
 
C. High risk, less symptoms: baseline CAT < 10 AND either GOLD Grade 3-4 OR ≥ 2 exacerbations, prior year OR >=1 exacerbation leading to hospitalization, prior year
 
D. High risk, more symptoms: baseline CAT >= 10 AND either GOLD Grade 3-4 OR ≥ 2 exacerbations, prior year OR >=1 exacerbation leading to hospitalization, prior year
 
 
 

Baseline Characteristics
Participant Disposition

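### Per Protocol exclusion 02, read literally, removes every participant with exactly one historical exacerbation, including those whom inclusion 4 admits

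*SAP*

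**What the plan says.** Inclusion 4 (Protocol 6.1) can be met in either of two ways over the 12 months before screening: two or more qualifying exacerbations, or one qualifying exacerbation together with fibrinogen of at least 3 g/L. The second route ends "outpatient center and a plasma fibrinogen concentration at screening" at or above that threshold. The Schedule of Activities supports this route: the pre-screening fibrinogen test is "only required for participants with 1 COPD exacerbation in the prior year".

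SAP 14.1.1 drops a participant from PP if any one listed criterion is met. Row 02, labelled as relating to inclusion 4, reads "< 2$ historical exacerbations or one historical exacerbation with screening fibrinogen $< 3$ g/L".

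SAP 4.1 defines PP as "All participants from the mITT population who did not have a protocol deviation considered to impact efficacy". The primary estimand in SAP 7.1.1 concerns "the population of participants who did not experience a protocol deviation considered to impact efficacy and completed six months of treatment", and SAP 7.1.1.3 names PP as the population for that analysis.

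Elsewhere the SAP expects participants with fewer than two events in PP. SAP 5.4.2 lists the subgroup "History of $\geq 2$ moderate/severe exacerbations vs $< 2$ moderate/severe exacerbation". The exacerbation-rate model in SAP 7.2.1.5.1, run on PP, includes "treatment group, gender, exacerbation history" with levels ≤1 and ≥2, as does the time-to-first-event model in 7.2.2.5.1. Interim Table 2.19, also on PP, has a stratum for exactly one moderate/severe event.

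**The concern.** Row 02 should pick out participants who fail inclusion 4. As worded, it also removes participants who pass by the second route. It therefore conflicts with the PP definition and the primary estimand, both of which remove people only for a deviation.

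PP carries the primary dose-response analysis. The ITT efficacy displays are marked as strategic interim only, and mITT is assigned to study-population and safety displays. The one contingent sensitivity population, in SAP 4.2, is a subset of PP. No E-RS model planned for the final analysis in a broader population would show the effect of the loss.

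Under literal coding the primary analysis would lose an eligible group defined at baseline. Precision would fall, and the result would describe essentially those with two or more historical exacerbations instead of the enrolled population. Because the rule uses baseline data only, it would not by itself unbalance the arms.

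**Working it through.** **Logic.** Let e be the number of historical exacerbations and f the screening fibrinogen in g/L.

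- Inclusion 4 is met if e ≥ 2, or (e = 1 and f ≥ 3).
- Row 02 excludes if e < 2, or (e = 1 and f < 3).

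Since e = 1 implies e < 2, row 02 reduces to e < 2.

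| e | f | Meets inclusion 4 | Excluded by row 02 | Consistent |
|---|---|---|---|---|
| 0 | any | no | yes | yes |
| 1 | 2.9 | no | yes | yes |
| 1 | 3.0 or 3.5 | yes | yes | **no** |
| 2 or more | any | yes | no | yes |

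If the first clause is changed to e < 1, the rule becomes the exact complement of inclusion 4.

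**Which events count.** Row 02 does not say which severities count. Inclusion 4 counts events that were treated, hospitalised or held for extended observation. For the model covariate, "The total number of moderate/severe exacerbations will be categorized as" ≤1 or ≥2 (SAP 14.6.2). If row 02 counted mild events as well, someone with one moderate/severe and one mild event would survive it. The ≤1 level would then be depleted, not necessarily empty.

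**Size, if coded literally.** Inputs from the protocol are 540 expected completers (5.2), SD 6.5 and the Table 4 means (10.2), six equal arms, and 90% intervals. The proportion s with one exacerbation is not reported; 10%, 20%, 40% and 60% are assumed. All of them are taken to be removed.

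Remaining N = 540 × (1 − s) = 486, 432, 324, 216.

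The calculation simulates a Bayesian 3-parameter Emax model without covariates. It uses a functional uniform prior on ED50 over the SAP dose grid, N(0, 100²) on Emax, and near-flat priors on E0 and the residual variance. There are 6,000 trials per cell, giving a Monte Carlo standard error of at most 0.007.

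Protocol 10.2 states over 80% at 35 mg in all scenarios with 600 participants. With all 600 analysed, scenario 2, the least favourable at that dose, gives 0.85, which agrees.

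Chance that the 90% credible interval for 35 mg versus placebo lies below zero:

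| N analysed | Scenario 1 | Scenario 2 | Scenario 3 | Mean half-width, scenario 2 |
|---|---|---|---|---|
| 540 | 0.99 | 0.82 | 0.88 | 1.11 |
| 486 | 0.97 | 0.78 | 0.84 | 1.17 |
| 432 | 0.96 | 0.72 | 0.81 | 1.24 |
| 324 | 0.91 | 0.64 | 0.69 | 1.43 |
| 216 | 0.78 | 0.49 | 0.54 | 1.76 |

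**Check on the widening.** For a simple pairwise comparison, half-width = 1.645 × 6.5 × √(2/n). With n = 540/6 = 90 this is 1.59. At s = 10% (n = 81) it is 1.68, and at s = 40% (n = 54) it is 2.06. The ratio is 1/√(1 − s), so 1.05 and 1.29. The simulated ratios are 1.17/1.11 = 1.05 and 1.43/1.11 = 1.29.

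**The case against.** The strongest reply is that this is a wording slip whose meaning is clear. The row carries the inclusion 4 label, its fibrinogen clause has a purpose only if eligible one-exacerbation participants stay in, and the PP definition and planned strata point the same way. SAP 4.3 also says deviations are handled under a separate management plan and dataset, so the coding cannot be seen. All of this stands as evidence of intent. It does not change the rule as written, which is complete and programmable: a programmer and a checker following it could agree and both be wrong.

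Some displays could expose literal coding. These include exacerbation history in mITT and PP (interim Tables 1.11/1.12, final 1.21/1.22), population counts (interim 1.5, final 1.10), PP exclusions (final 1.11), interim Tables 2.19 and 2.42, and Listings 6 and 9. This makes silent loss of a whole group less likely, but it relies on someone noticing.

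The size is hypothetical and depends on modelling choices. The share is assumed, other PP exclusions and the 10-day diary rule would already reduce 540, and the SAP chooses among three models. The SAP can also be read as basing the functional uniform prior on all model parameters. One such reading gives about 0.90, 0.86 and 0.66 in scenario 2 at N = 540, 432 and 216. The levels are higher and scenario 2 stays above 80% with 20% removed, but the decline is similar in size. The tabulated probabilities are therefore illustrative.

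**Conclusion.** The concern holds. On its wording, row 02 excludes eligible participants and contradicts inclusion 4, the PP definition, the primary estimand and the planned strata. That is certain. Whether anyone was actually removed is not established, because the flag coding is not in the documents.

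If it was coded literally, the loss is the whole one-exacerbation group, or most of it if mild events count towards row 02. Half-widths would grow by roughly 1/√(1 − s): about 5% at a 10% share and about 29% at 40%. Under the simulated model and prior, scenario 2 falls below the 80% design level even at a 10% share; under the alternative prior reading it does not do so at 20%. This should be corrected because the row defines the primary-analysis population.

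**What to change.** Replace row 02 with the complement of inclusion 4: no qualifying historical exacerbation, or exactly one qualifying historical exacerbation with screening fibrinogen below 3 g/L. State that qualifying events are counted as inclusion 4 counts them, including extended observation.

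Before the final database freeze, check the PP flag code against this text. A cross-tabulation of the flag by exacerbation count and fibrinogen is enough. Confirm and record which reading was used for PP at the strategic interim already performed.

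The cost is one line of SAP text and a short programming check. No data collection or model changes.
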